Given that only modestly higher PD responses were observed with 10 mg QD dosing relative to the 20 mg QW dose in Study MB130-045, and the consideration that a QW SC dosing regimen is likely to be more acceptable to participants than a daily dosing regimen, and therefore be associated with better compliance, 3 weekly doses were identified -i.e., 10 mg, 20 mg, and 40 mg QW, that are expected to achieve clinically meaningful responses for key biomarkers of NASH, and can be administered in up to 2 injections. Model-predicted percent change from Baseline in key biomarkers for typical NASH study participants are noted in [Table 4](#) below.

Table 4 Model-Predicted Percent Change from Baseline in Key Biomarkers for Typical Participants with NASH

Biomarker	Model-predicted typical % change in response at trough concentrations with various QW doses of BMS-986036		
	10 mg QW	20 mg QW	40 mg QW
Hepatic fat content	-24.8	-29.7	-31.9
Alanine aminotransferase	-16.7	-22.6	-26.7
PRO-C3	-7.0	-12.4	-17.4
Adiponectin	11.4	18.3	24.0

NASH = nonalcoholic steatohepatitis; PRO-C3 = N-terminal type 3 collagen propeptide; QW = once weekly

The safety and PK of 20 mg QW and 40 mg QW dosing regimens for 3 weekly doses has been recently characterized in a Phase 1 study in obese healthy Japanese participants. Preliminary results show that exposure is generally dose proportional between 20 mg and 40 mg QW, and the 40 mg QW dose was safe and well tolerated (refer to IB for additional details). The 40 mg QW dose is hypothesized to provide increased efficacy compared to that of the 20 mg QW dose, but with lower overall BMS-986036 exposure than that of the 10 mg QD dose. Additionally, compared to 10 mg QD, the 40 mg QW dose is expected to provide a higher margin relative to the exposure associated with nonclinical bone-related AEs, and it also provides a lower burden of PEG. Evaluation of the 10 mg QW and 40 mg QW dose regimens is expected to facilitate a more complete evaluation of the dose-response profile of BMS-986036.

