Any pregnancy that occurs in a female partner of a male study participant should be reported to sponsor or designee during at least 5 half-lives after product administration (5 days) plus 30 days (duration of ovulatory cycle) for a total of 35 days after the end of the Double-Blind Treatment Period. In order for the sponsor or designee to collect any pregnancy surveillance information from the female partner, the female partner must sign an ICF for disclosure of

this information. Information on this pregnancy will be collected on the Pregnancy Surveillance Form.

Laboratory Test Result Abnormalities

The following laboratory test result abnormalities should be captured on the nonserious AE eCRF page or SAE eCRF page, as appropriate. Paper forms are to be used only in the event that the electronic system is not functioning.

- Any laboratory test result that is clinically significant or meets the definition of an SAE
- Any laboratory test result abnormality that required the participant to have study medication discontinued or interrupted
- Any laboratory test result abnormality that required the participant to receive specific corrective therapy

It is expected that wherever possible, the clinical rather than laboratory term would be used by the reporting investigator (e.g., anemia versus low hemoglobin value).

Potential Drug-Induced Liver Injury

Wherever possible, timely confirmation of initial liver-related laboratory abnormalities should occur prior to the reporting of a potential DILI event. All occurrences of potential DILIs, meeting the defined criteria, must be reported as SAEs (see [Appendix 9](#) for reporting details). **Repeat laboratory testing may be performed locally**, and the results should be promptly communicated to the investigator site.

For the purpose of evaluating a potential DILI, the Baseline value is defined as the mean of the test results from analysis of samples collected during Screening and on Day 1.

Note that the evaluation processes below do not replace SAE reporting per defined criteria in [Appendix 9](#).

Evaluation of Participants with New Elevations of Aminotransferases and/or Total Bilirubin
Repeat laboratory testing (including ALT, AST, fractionated bilirubin and alkaline phosphatase) and physical examination should be performed within 48-72 hours when:

- Participants with normal Baseline aminotransferase (ALT and/or AST) values develop elevations greater than $3\times$ the ULN based upon the central lab, or

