Urinalysis (to be collected at each visit through the Week 52/PTFU Visit):

- pH
- Specific gravity
- Protein [REDACTED]
- Glucose
- Ketones
- Blood
- Leukocyte esterase
- Nitrite
- Creatinine [REDACTED]
- Albumin [REDACTED]
- Microscopic examination (only to follow-up abnormal findings)
- Drug Screen (Screening only)

Immunogenicity (to be collected at Day 1 and each subsequent visit through the Week 52/PTFU Visit and at Long-Term Immunogenicity Follow-Up Visits as applicable [see Section 8.5.3.6]):

- Serum anti-BMS-986036 antibody
- Serum anti-FGF21 antibody

PRO-C3 (to be collected at Screening, Day 1, Week 4, Week 8, Week 12, Week 24, Week 48/ET, and Week 52 [PTFU]). Participants will fast for 8 hours prior to collection of blood samples for these assessments:

- N-terminal type 3 collagen propeptide (PRO-C3) – Will include blood collection for additional serum for new or improved assays

Adiponectin (to be collected at Screening, Day 1, Week 4, Week 8, Week 12, Week 24, Week 48/ET, and Week 52/PTFU). Participants will fast for 8 hours prior to collection of blood samples for these assessments

Plasma and Serum for disease, target and drug effect biomarkers (to be collected at Day 1, Week 4, Week 8, Week 12, Week 24, Week 48, ET [if applicable], Week 52/PTFU, and 6 months after Week 52/PTFU). Participants will fast for 8 hours prior to collection of these samples

Gene Expression (to be collected at Screening, Day 1, Week 4, Week 8, Week 12, Week 24, and Week 48/ET and Week 52/PTFU):

- Whole blood for RNA analysis (broad and/or directed gene expression profiling)

Micro RNA (miRNA) (to be collected at Screening, Day 1, Week 4, Week 8, Week 12, Week 24, Week 48/ET, and Week 52/PTFU)

ALT = alanine aminotransferase; APRI = AST-Platelet Ratio Index;
AST = aspartate aminotransferase; DNA = deoxyribonucleic acid; β -HCG = beta human chorionic
gonadotropin; ELF = Enhanced Liver Fibrosis; ET = early termination; FGF21 = fibroblast growth factor
21; FIB4 = Fibrosis 4 Index; NAFLD = nonalcoholic fatty liver disease; NAS = NAFLD Activity Score;
NASH = nonalcoholic steatohepatitis; PTFU = Post-Treatment Follow-up; RNA = ribonucleic acid;

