For continuous endpoints the analysis of covariance (ANCOVA) models will be used to explore changes from baseline that include fixed factors for the treatment group and the corresponding covariate for baseline value for the following:

- Quantitative measurements of fibrosis and fat on biopsy
  - Assessment of qFibrosis using digital pathology
  - Assessment of CPA
  - Assessment of fat and alpha-SMA by morphometry
- Hepatic fat fraction as measured using MRI-PDFF
- Noninvasive measures of fibrosis and/or cirrhosis
  - Liver stiffness as determined by MRE
  - Fibroscan elastography results
  - APRI, FIB-4, and NAFLD scores
- Exploratory biomarkers
  - Transaminases ALT and AST
  - PRO-C3

A repeated measures analysis will model changes from baseline for each of the exploratory endpoints separately for data collected at planned visits using restricted maximum likelihood estimations. The model will include treatment group, visit, baseline value, treatment \* visit and baseline stratification factors as fixed effects. An unstructured covariance matrix will be used to represent the correlation of the repeated measures within each subject. This model will be used to provide point estimates for the treatment differences, standard errors for the differences, and corresponding 2-sided 95% confidence intervals for mean change from baseline at each time point. Statistical inferences for comparing treatment groups will utilize Kenward-Rodgers Degrees of Freedom.

Other biomarkers will be descriptively summarized by time point and will include percent change from baseline in addition to change from baseline.

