## 8.0 Conventions and General Definitions

### 8.1 General Definitions

Term	Definition
Study Day	Study day is calculated as: assessment date – date of first dose + 1
Baseline	Unless otherwise stated, Baseline is defined as the last measurement prior to dosing on Day 1 (Week 0). If the measurement on Day 1 is missing or not available, then a prior measurement during the screening period may be used as baseline.
Change from Baseline	Change from baseline is defined as (value at post-baseline visit – value at baseline).
Change in the maximum post-baseline value	Change from baseline in the maximum post-baseline value is defined as highest observed value post-baseline. The change is calculated using this value as the post-baseline value.
Percent Change from Baseline	Percent change from baseline is defined as $([\text{value at post-baseline visit} - \text{value at baseline}]/\text{value at baseline}) \times 100$ . If the baseline value is 0 and the post-baseline value is also 0, then the percent change from baseline is set to 0. Percent change from baseline is not calculated if the baseline value is zero or baseline or post-baseline value is missing.
Study Treatment	For the purposes of the calculations included in this SAP, study treatment will include only doses of BMS-986036 (dose levels of 10 mg QW, 20 mg QW or 40 mg QW) or placebo QW.
Duration of Study Treatment (weeks)	Duration of study treatment in weeks will be defined as: (date of last dose of study treatment – date of first dose of study treatment + 7) / 7.
Treatment Completion (%)	Treatment completion (%) will be calculated as the total number of weeks of treatment received divided by the total number of expected doses (48), multiplied by 100.
End of Study (EOS) Date	The EOS date is the date recorded on the eCRF that a participant either discontinued or completed the study. If the participant is lost

Sponsor: Bristol-Myers Squibb

Protocol No.: MB130-069

	to follow-up, the EOS date will be the date of the last visit assessment obtained.
First Dose Date – Study	The date a participant received their first dose as recorded in the eCRF as date study treatment was administered.
Last Dose Date – Study	The date of last recorded dose on the eCRF for a subject.

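### The exploratory models for PRO-C3 and ALT use raw-scale change from a single pre-dose value; they are valid, but a log-scale model that also uses the Screening sample would probably be more precise

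*SAP*

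**What the plan says.** SAP 6.4 sets out two models. The first is an ANCOVA with treatment and baseline value: "For continuous endpoints the analysis of covariance (ANCOVA) models will be used to explore changes from baseline". Its list includes ALT, AST, PRO-C3, APRI, FIB-4 and the NAFLD score. The second is wider: "A repeated measures analysis will model changes from baseline for each of the exploratory endpoints separately". Neither names a log transformation or a ratio.

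SAP 8.1 fixes the scale: "Change from baseline is defined as (value at post-baseline visit – value at baseline"). Percent change is a separate term there. The same section fixes the reference value: "Unless otherwise stated, Baseline is defined as the last measurement prior to dosing on Day 1 (Week 0"). A Screening measurement may stand in only when the Day 1 value is missing.

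Protocol 6.2.2 introduces Table 4 as the "Model-predicted percent change from Baseline in key biomarkers for typical NASH study participants". For 10, 20 and 40 mg it gives ALT -16.7, -22.6 and -26.7, and PRO-C3 -7.0, -12.4 and -17.4. It also covers hepatic fat and adiponectin.

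Protocol Table 8 reads "PRO-C3 (to be collected at Screening, Day 1, Week 4, Week 8", so two pre-dose PRO-C3 samples exist. Blood chemistry is also taken at Screening (Table 1) and Day 1 (Table 2). For potential drug-induced liver injury, Protocol 8.5.3.1 uses both samples: "the Baseline value is defined as the mean of the test results from analysis of samples collected during Screening and on Day 1".

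SAP 4.5 lists percent change for MRI-PDFF, MRE, FIB-4, APRI and adiponectin, but not for ALT, AST or PRO-C3.

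**The concern.** If a drug lowers a positive marker by a fixed percentage, the absolute fall is larger in participants who start high. Raw-scale change then mixes effect size with baseline level, and the few high values dominate the error term. A wide ALT and AST range is possible here, since values up to 5 times the upper limit of normal are eligible (Protocol 8.3.2). The modelled result is also not on the scale in which the dose rationale is expressed.

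Separately, a single pre-dose measurement carries assay and day-to-day noise. A second one is already in hand and could absorb part of it.

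What is at stake is precision. Protocol 6.2.1 bases the design and dose selection of Phase 3 on the totality of efficacy, safety and PK from this study and its companion, and it wants more data on PRO-C3 as a pharmacodynamic marker. With about 38 per arm, recoverable precision is worth having.

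**Working it through.** **The plan's own figure.** The documents give no power for the biomarker models. The only power statement (Protocol 9.1: at least 70% for the trend test on the primary endpoint, 25 per arm, one-sided 0.05) reproduces at 70.1% asymptotically with equally spaced scores. It does not bear on this point.

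**Inputs from the documents.** About 38 per arm (Protocol 6.2); 40 mg effects of -17.4% for PRO-C3 and -26.7% for ALT (Table 4); two-sided 95% intervals (SAP 6.4).

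**Inputs assumed.** Log-normal values; a multiplicative effect; no change on placebo (Table 4 has no placebo column); CV 30-80%. Let *r* be the correlation of each baseline with follow-up, and *q* the correlation between Screening and Day 1.

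**Step 1: value of the second baseline.** Residual variance is proportional to 1 - r² with one baseline and to 1 - 2r²/(1+q) with both.

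- All correlations equal: r = q = 0.6 gives 0.640 against 0.550, a cut of 14%; r = q = 0.7 gives 0.510 against 0.424, a cut of 17%; r = q = 0.8 gives 0.360 against 0.289, a cut of 20%.
- Screening and Day 1 closer to each other than to follow-up: (r, q) = (0.6, 0.8) cuts 6%; (0.6, 0.9) cuts 3%; (0.7, 0.9) cuts 5%; (0.7, 0.8) cuts 11%.

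**Step 2: log-scale power by hand.** Take PRO-C3 at CV 60% with r = q = 0.7. The log SD is √ln(1 + 0.6²) = √0.3075 = 0.5545, and the effect is ln(1 - 0.174) = -0.191.

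- One baseline: SE = 0.5545 × √0.510 × √(2/38) = 0.0909. Then 0.191/0.0909 = 2.10; subtracting the critical value 1.99 leaves 0.11, so power is about 54%.
- Both baselines: SE = 0.5545 × √0.424 × √(2/38) = 0.0828. Then 2.31 - 1.99 = 0.32, so power is about 62%.

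Simulation of the same two cases gives 55% and 61%. The planned raw-scale model with Day 1 alone has no closed form; simulated, it gives 46%.

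**Step 3: simulated power, 40 mg versus placebo.** In each range one end is r = 0.6, q = 0.8 and the other is r = q = 0.7. Repeat runs agree within about 2 points.

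| Marker | CV | Planned: raw, Day 1 | Log, both baselines |
|---|---|---|---|
| PRO-C3 -17.4% | 30% | 92-97% | 95-99% |
| PRO-C3 -17.4% | 60% | 38-46% | 47-61% |
| PRO-C3 -17.4% | 80% | 24-28% | 32-43% |
| ALT -26.7% | 60% | 77-85% | 87-95% |
| ALT -26.7% | 80% | 53-61% | 68-82% |

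For ALT at CV 30% both models are at 100%. Under no effect at CV 80%, rejection was 4.7% (planned) and 5.2% (log, both), so the gain does not come from inflated error.

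**Step 4: which change does the work.** These runs averaged the two baselines.

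| Setting | Raw, Day 1 | Log, Day 1 | Log, both |
|---|---|---|---|
| PRO-C3, CV 50%, r 0.6, q 0.8 | 51.9% | 57.8% | 61.0% |
| PRO-C3, CV 50%, r = q = 0.6 | 51.9% | 57.9% | 64.1% |
| ALT, CV 80%, r 0.6, q 0.8 | 52.6% | 65.3% | 67.8% |

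With unequal correlations the log scale supplies most of the gain (5.9 of 9.1 points in the first row, 12.7 of 15.2 in the third). With equal correlations the two shares in the second row are about even (6.0 and 6.2 points). At CV 30% both are small.

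**The case against.** The strongest reply is that the advantage is partly built in: the simulated data follow the model that the fix assumes, and no CV, correlation or skewness is in the documents. That stands, which is why the result is a range that includes almost nothing at CV 30%. The simulation is also a two-arm, single-visit comparison; the planned repeated-measures model, with its visits and stratification factors, was not simulated.

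The second-baseline gain is open to the same challenge. Screening falls at most 8 to 12 weeks before Day 1, while follow-up runs to Week 48 on treatment, so the two pre-dose values may well correlate more closely with each other. The 14-20% variance cut is therefore the favourable case. The liver-injury baseline is a safety rule, and Protocol 9.4.4 itself names Day 1 predose as Baseline for ALT, AST and PRO-C3; the averaging shows that both samples are considered usable, no more.

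Four stronger readings are tempting but not supported:

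- *The planned models are invalid.* They are not: randomised ANCOVA on raw change estimates a mean difference properly.
- *Table 4 cannot be checked.* Too strong. Protocol 9.5.4 sends population PK-PD and exposure-response work to a separate pharmacometric plan, and an approximate percent change of means can be derived from the planned ALT and PRO-C3 summaries.
- *Percent effects are predicted for every marker.* Table 4 has no entry for AST, FIB-4 or APRI; they come in by analogy.
- *All the fibrosis indices lose precision.* The NAFLD Fibrosis Score can be negative, so a log does not suit it. ELF is not in the ANCOVA list and has no Screening sample. FIB-4 and APRI are scheduled from Day 1, although their components are measured at Screening.

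**Conclusion.** The point holds as one of efficiency and interpretability for PRO-C3 and ALT, and by analogy for AST, FIB-4 and APRI. The plan models raw change from one pre-dose value, the dose rationale speaks in percentages, and a second pre-dose value sits unused unless Day 1 is missing.

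For PRO-C3 the power gain is about 2-3 points at CV 30%, 9-15 at CV 60% and 8-15 at CV 80%. For ALT it is nil at CV 30%, about 10 at CV 60% and 15-21 at CV 80%. These figures rest on log-normal data, a multiplicative effect, no placebo change, complete data on 38 per arm, and both baselines equally correlated with follow-up. The second baseline alone cuts residual variance by 14-20% if all correlations are equal (0.6-0.8), and by about 3-11% if Screening and Day 1 are closer to each other.

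The endpoints are exploratory, and the primary and secondary analyses are untouched. The change is worth making but does not affect the trial's main conclusion.

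**What to change.** In SAP 6.4, fixed before unblinding so that the scale is not chosen after seeing results:

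- For PRO-C3, ALT, AST, FIB-4, APRI and (in the repeated-measures model) adiponectin, model log(post/baseline) with log baseline as covariate. Report geometric mean percent change and the ratio to placebo with 95% CI. Keep the raw-scale summaries.
- Where Screening and Day 1 values both exist, add the log of the last Screening value before Day 1 as a second covariate, substituting the Day 1 value if it is missing. Keep Day 1 as Baseline for the change, as Protocol 9.4.4 has it.
- For MRI-PDFF, use the log of its Screening baseline only; there is no Day 1 scan.
- Keep the raw scale for scores that can be zero or negative, such as the NAFLD Fibrosis Score.
- Reconcile Protocol 8.5.1, which lists PRO-C3 and adiponectin from Day 1, with Tables 1 and 8, which list both from Screening.

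The cost is SAP wording and programming, with no new samples. There are two downsides. The target becomes a geometric mean ratio rather than a mean difference. A rule is also needed for Screening samples that were repeated (Protocol 8.3.8.1) or carried over from the companion study or an earlier screening (8.3.8.2).

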## 2.3 Randomization

Randomization will be conducted in the following manner:

Participants will be stratified at randomization by country (Non-Japan versus Japan). Participants in countries other than Japan will be stratified at randomization according to Type 2 Diabetes Mellitus (T2DM) status (yes versus no). Japanese participants will not be further stratified.

- Eligible participants will be randomized by the IRT using a prespecified schedule in a double-blind manner to 10 mg BMS-986036, 20 mg BMS-986036, 40 mg BMS-986036, or placebo arms in a 1:1:1:1 ratio based on the stratification factors specified in [Section 2.1](#).
- The IRT will provide study treatment kit numbers that contain the appropriate study treatment (BMS-986036 or placebo) for dispensation to that participant.

At subsequent study visits, the investigator or designee will access the IRT to receive the corresponding kit numbers assigned to the participant for the purpose of dispensing study treatment.

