#### 4.5 Exploratory Endpoints

Exploratory endpoints include the following:

- Quantitative measurements of fibrosis and fat on biopsy
  - Assessment of NASH CRN Fibrosis Score at Week 48
    - Proportion of participants with  $\geq 1$  stage improvement
    - Proportion of participants with  $\geq 2$  stage improvement
    - Proportion of participants with  $\geq 2$  stage improvement without worsening of NASH
    - Changes in Fibrosis (as expressed by Shift from baseline)
    - Proportion of participants with  $\geq 1$  stage improvement, no change, or worsening
  - Assessment of Ishak Fibrosis Score at Week 48
    - Proportion of participants with  $\geq 2$  stage improvement
    - Changes in Fibrosis (as expressed by Shift from baseline)
    - Proportion of participants with  $\geq 1$  stage improvement, no change, or worsening
  - Assessment of qFibrosis using digital pathology at Week 48
    - Absolute, percent change, and change from baseline
  - Assessment of CPA at Week 48
    - Proportion of participants with any improvement
    - Absolute, percent change, and change from baseline
  - Assessment of fat and alpha-SMA in stained tissue by morphometry at Week 48
    - Absolute, percent change, and change from baseline
- Assessment of NAS score at Week 48
  - Changes in NAS (as expressed by shift from baseline, for each individual NAS components (Steatosis, inflammation, Ballooning) as well as Total score)
  - Proportion of participants with improvement, no change, or worsening in NAS Total
- Hepatic fat fraction as measured using MRI-PDFF at Week 24 and Week 48
  - Absolute, percent change, and change from baseline
  - Proportion of subjects in each treatment group with  $\geq 30\%$  relative reduction,  $\geq 20\%$  relative reduction,  $\geq 10\%$  relative reduction, and  $\geq 5\%$  absolute reduction
- Noninvasive measures of fibrosis and/or cirrhosis
  - Liver stiffness as determined by Magnetic Resonance Elastography (MRE) at Week 24 and Week 48
    - Absolute, percent change, and change from baseline
    - Proportion of subjects in each treatment group with  $\geq 19\%$  or  $\geq 15\%$  reduction
  - Fibroscan elastography results at Week 48
    - Absolute, percent change, and change from baseline
    - Proportion of subjects in each treatment group with any decrease by time point

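### The exploratory ANCOVA in SAP 6.4 omits the randomisation strata that the repeated-measures model beside it includes, and no lead model is named; if the strata are prognostic, its standard errors are somewhat too large.

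*SAP*

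**What the plan says.** **Randomisation.** Protocol 9.3 and SAP 2.3 stratify by Japan/Non-Japan, with a further split by T2DM outside Japan only; "Japanese participants will not be further stratified". This gives three cells: Japan, Non-Japan with T2DM, and Non-Japan without T2DM.

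**ANCOVA.** SAP 6.4 lists qFibrosis, CPA, morphometric fat and alpha-SMA, MRI-PDFF, MRE, Fibroscan, APRI, FIB-4, the NAFLD score, ALT, AST and PRO-C3. The models for these "include fixed factors for the treatment group and the corresponding covariate for baseline value". No stratum term appears, and no confidence interval is specified for this model.

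**Repeated measures.** The next paragraph of SAP 6.4 begins: "A repeated measures analysis will model changes from baseline for each of the exploratory endpoints separately for data collected at planned visits". Its terms are treatment, visit, their interaction and the baseline value, plus "baseline stratification factors as fixed effects". It promises standard errors and "corresponding 2-sided 95% confidence intervals for mean change from baseline at each time point".

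**Visits.** Protocol 8.5.1 has biopsy and Fibroscan at Screening and at Week 48/ET only, and SAP 4.5 lists "Fibroscan elastography results at Week 48". Under SAP 6.4 an ET biopsy counts as Week 48, while ET results for non-biopsy endpoints are summarised separately. Either way, each of these endpoints has one planned post-baseline time point.

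**Elsewhere.** Both sensitivity analyses of the primary endpoint in SAP 6.1.1.1 (logistic regression and extended CMH) use the strata.

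**The concern.** Stratified randomisation balances the strata across arms, so a treatment difference is already protected from their influence. A model without the strata does not take credit for this. It leaves the between-stratum variance in the residual and reports a standard error larger than the estimate's real variability. Intervals then cover more than 95% of the time and tests lose some power.

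The SAP gives no reason for adjusting in one model and not in the model next to it. For endpoints measured at several visits, the repeated-measures model supplies an adjusted estimate in any case. For the single-visit biopsy and Fibroscan endpoints there is nothing to repeat, so ANCOVA is the model an analyst would naturally use, and it is the one without the strata. Protocol 8.5.1.1 notes that pathologists' staging varies considerably within and between readers, and presents CPA as a quantitative alternative, so precision on these measures has some value.

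The covariate mismatch also leaves a choice open. An endpoint could be analysed with or without strata, and nothing says which result leads.

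**Working it through.** **The plan's own figure.** The documents give one power figure: at least 70% for the primary Cochran-Armitage test (Protocol 9.1; 25 per arm, rates 15/20/30/40%, one-sided 0.05). With scores 0, 1, 2, 3 centred at 1.5:

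- T = 25 × (−1.5×0.15 − 0.5×0.20 + 0.5×0.30 + 1.5×0.40) = 10.625
- null variance = 0.2625 × 0.7375 × 25 × 5 = 24.20
- alternative variance = 22.98
- power = Φ[(10.625 − 1.645×√24.20)/√22.98] = 70.1%

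The figure reproduces, but it concerns the primary endpoint and does not bear on this point. No power or precision figure exists for the ANCOVA.

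**Inputs.**

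- N = 155 (Protocol 9.1), four arms at 1:1:1:1, three strata (SAP 2.3).
- The ANCOVA without strata uses 5 parameters (intercept, three treatment contrasts, baseline), so 150 residual df. Adding the strata uses 2 more, so 148 df.
- Assumed, because the documents do not give it: R², the share of residual variance the strata explain after treatment and baseline, from 0 to 20%.

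**Formula.** With strata balanced across arms,

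width without strata / width with strata = t(0.975, 150) / [t(0.975, 148) × √(1 − R²)]

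Here t(0.975, 150) = 1.97591 and t(0.975, 148) = 1.97612, a ratio of 0.99989.

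| Assumed R² | √(1 − R²) | Extra width without strata |
|---|---|---|
| 0% | 1.0000 | −0.01% |
| 1% | 0.9950 | +0.49% |
| 2% | 0.9899 | +1.00% |
| 5% | 0.9747 | +2.59% |
| 10% | 0.9487 | +5.40% |
| 20% | 0.8944 | +11.79% |

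With N = 100, 124 or 109 (the planned size, and 155 less an assumed 20% or 30%), the figures stay within 0.03 percentage points of these.

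**Simulation check.** Stratified blocked randomisation (block size 4 assumed), 4,000 runs per setting, two assumed stratum splits (24/33/98 and 12/36/107):

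- *No missing data.* Extra width is 0.5% at R² = 1%, 2.6–2.7% at 5%, 5.5% at 10% and 12.1% at 20%. Coverage without strata is about 96% at R² = 10% and 97% at 20%. The true spread of the estimate is at most 0.14% larger without strata, so the loss lies in the reported standard error.
- *20% missing at random (assumed).* Extra width is 2.4–2.5% at R² = 5% and 5.3–5.4% at 10%. Missing data disturb the balance, so adjustment now also reduces the true spread a little: it is 1.4–1.5% larger without strata at R² = 10%.
- *Cost if the strata explain nothing.* Adding them widens the interval by at most 0.02% with complete data and by about 0.2% with 20% missing.

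**The repeated-measures model at one visit.** Visit and its interaction with treatment drop out, and the unstructured covariance becomes a single variance. Treatment, baseline and strata remain, which is an ANCOVA with strata. SAP 6.4 can therefore be read as specifying both an unadjusted and an adjusted model for the same endpoint and visit.

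**The case against.** The strongest reply is that the adjusted analysis is already planned. The repeated-measures sentence excludes no endpoint, and at one visit the model reduces to the ANCOVA with strata proposed here. The only standard errors and 95% intervals that SAP 6.4 promises belong to that model. A reader might infer that the unadjusted ANCOVA is the sole model for biopsy and Fibroscan, and that their reported intervals must therefore be too wide. The documents do not support that. What survives is the ambiguity: two covariate sets may apply to the same endpoint, and the SAP does not say which leads or whether a repeated-measures model is meant for single-visit data.

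The second reply is that the size is assumed. This stands. T2DM may well be related to the level of liver fat or fibrosis, but the baseline covariate absorbs part of that, and only the association with remaining change counts. The documents give no figure for it. At R² of 1–2% the effect is 0.5–1.0%.

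Third, nothing is biased and no false-positive risk is added. That also stands: the unadjusted analysis errs on the cautious side. The endpoints are exploratory, in a Phase 2 study with no multiplicity control (SAP 6.1.3), and the primary trend test is itself unadjusted, so adjustment is not a rule the SAP follows everywhere.

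**Conclusion.** The inconsistency is real and small. The exploratory ANCOVA omits factors used in the randomisation, while the repeated-measures model beside it includes them, and no reason or order of precedence is given. If the strata predict change after baseline adjustment, the ANCOVA's standard errors are too large and its inference is conservative. Intervals would be about 0.5% wider at a partial R² of 1%, 2.6% at 5% and 5.4% at 10%, and no wider at 0%; the excess passes 10% only near an R² of 20%. These sizes rest on an assumed R² and on balance of the strata across arms.

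It would go too far to say that the biopsy and Fibroscan endpoints certainly get needlessly wide intervals, or that their inference is invalid. The first depends on an R² the documents do not give and on which of two models is reported. The second is contradicted by the conservative direction of the effect. Severity is low: only exploratory endpoints are touched, and the primary and secondary analyses are unaffected.

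**What to change.** In SAP 6.4:

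1. Set the ANCOVA terms to treatment group, baseline value and randomisation stratum, coded as one three-level factor (Japan; Non-Japan T2DM yes; Non-Japan T2DM no), because T2DM was not a stratum within Japan. If the strata are left out on purpose, give the reason.
2. Name this ANCOVA as the model for endpoints with one planned post-baseline time point: qFibrosis, CPA, morphometric fat, alpha-SMA and Fibroscan.
3. For endpoints with several visits, state whether the ANCOVA or the repeated-measures model leads.

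The cost is a few lines of wording and two degrees of freedom. The strata are already recorded for randomisation. At worst, with strata that explain nothing and 20% of data missing, intervals widen by about 0.2%.
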